7.8. Off Treatment Criteria

Participants may stop taking atorvastatin for the following reasons: completed the protocol-prescribed intervention, adverse event or serious adverse event, inadequate agent supply, concomitant medications, medical contraindication, or interruption of chemotherapy due to adverse events or death.

Participants will continue to be followed, if possible, for safety reasons and in order to collect endpoint data according to the schedule of events. The study is designed to account for drop-outs due to poor health or death or loss to follow-up; thus, there will be no replacement of subjects that must drop out of the study after enrollment.

7.9 Off-Study Criteria

Participants may go 'off-study' for the following reasons: the protocol intervention and any protocol-required follow-up period is completed, adverse event/serious adverse event, lost to follow-up, concomitant medication, medical contraindication, withdraw consent, or death.

Since the study inception and development of the inclusion/exclusion criteria, guidelines regarding the potential administration of statins have been released by the ACC/AHA on November 12, 2013. These new guidelines suggest the use of a calculator to assess cardiovascular risk with subsequent initiation of statin therapy based on that risk. Concomitant with the release of the guidelines, however, have been several articles suggesting that the calibration of the calculator was somewhat imperfect, particularly in regards to data from both the Nurses' Health and Physicians' Health studies.

As a result of these controversies, the study investigators elected to leave the initial entry and exclusion criteria intact. Importantly however, their respective primary care physician will be mailed a letter raising their awareness to the publication of these guidelines. If the study participant and their primary care physician elect to initiate statin therapy, they will be counseled to stop their study drug and notify the respective investigators at their study site. They will still be allowed to participate in all other aspects of the trial as an open label statin user. Data analyses regarding intention to treat as well as treatment effect will be performed.

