4.4. Recruitment and Retention Plan

- 4.4.1 Over 600 breast and lymphoma patients should be eligible for enrollment among the NCORP sites, approximately 14% of whom will be males. Assuming conservatively that 17% (1 in 6) of the patients will consent to the study, we expect ~100 patients to be enrolled annually once the study is active at all planned sites. We will enroll 278 patients. We anticipate 28% of our cohort will drop out, so we expect 200 individuals to complete the study. In addition to NCORP sites, study enrollment will be opened to Alliance site members in which study coordinators, imaging expertise, and patient populations are readily available.
- 4.4.2. At each site, specific recruitment plans may include the following according to the site's institutional policy: screening clinic charts; tumor registry data; referral sources such as patient advocate groups, retirement communities, churches, support organizations, community organizations, newspapers, radio; or patient recruitment posters and recruitment letters.
- 4.4.3. The research PI or designee at each WF NCORP Research Base NCORP, which may include the clinic physician, resident, research nurse or research assistant, will review cancer registry and medical chart information to identify patients eligible for this protocol. Patients identified using these methods will be asked to join the study during their next clinic visit/consultation.

Accrual is expected to be 8 patients per month. Targeted accrual should be met in approximately 3 years for the 5 year study. A maximum of 278 patients will be enrolled on this trial. Patients will be followed for at least 24 months. Patients completing at least 24 months of study medication but no longer than 27 months will be followed for an additional 30 days after the last dose of study medication to evaluate any study related adverse events. After the Final assessment, the patient is no longer followed and data is no longer collected.

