5.6. Medication Modification

5.6.1 Medication Modification for Myalgias

Grade 1 Myalgias – If needed patient may take NSAIDs/analgesics at the discretion of the treating physician. Frequently this type of skeletal pain is not relieved with these medications.

Grade 2 or 3 Myalgias - Study medication should be held and patient instructed in the use of NSAIDs/analgesics per treating physician orders. ALT, AST and CK should be drawn within 24 hours.

- If labs are in acceptable range (ALT and AST are $< 3 \times \text{ULN}$ and CK $< 2.5 \times \text{ULN}$) study medication should be resumed.
- If Grade 2 or 3 myalgias redevelop, study medication should be discontinued. Patient will be considered off study medication but will continue to be followed.
- If ALT and/or AST are $> 3 \times \text{ULN}$ and/or CK $> 2.5 \times \text{ULN}$ study medication should be discontinued. Patient will be considered off study medication but will continue to be followed.

Any patient with suspected rhabdomyolysis/compartment syndrome of lower leg or rupture of tendon should stop the study medication immediately. The treating physician should assess the patient and order CK isoenzymes and/or other labs as deemed necessary. Patient will remain on study (off study medication) and be followed as usual.

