7.4. Evaluations at Completion of Study Intervention

All study participants will have an Cardiac MRI (see Section 7.2 for pregnancy testing prior to MRI exams) and blood drawn for a cardio profile, Lipids, CK, ALT, AST, Total Bilirubin, glucose, TSH, Hematocrit (only if gadolinium contrast is administered for the MRI procedure) and neurohormonal biomarkers noted in 7.3, between 24 – 27 months. Additional blood samples will be drawn on participants who consented to have blood stored for future research

Neurocognitive testing and Quality of Life Questionnaires will be obtained. Follow-up assessments will include laboratory evaluations, pill counts, and structured interviews assessing outcomes and potential adverse events.

7.5. Post-intervention Follow-up Period.

Patients completing 24 months of study medication will be followed for an additional 30 days after the last dose of study medication to evaluate any related adverse events. After the 25 month contact, the patient is no longer followed and data is no longer collected from the patient.

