7.7. Study Parameters Table

Study agent or placebo should be started when received. The patient must receive 2 doses prior to first chemotherapy tx. and those 2 doses may be given at least 12 hours apart. If necessary, due to time constraints, patient may be given 2 tablets at the same time at least 90 minutes prior to first chemotherapy tx. All evaluations/procedures are to be completed within + or – 30 days of specified time unless indicated otherwise. **Note: 24 month MRI should be obtained within 30 days prior to the last dose of study medication.**

Evaluation Procedure	Screening (C)	Baseline (D)	1 & 3 Mths (G)	6 Mths	12 Mths	18 Mths	between 24 - 27 Mths	1 Mth Post Final Assessment	
Informed Consent	X								
Demographics (p. 6 of enrollment form)	X								
Nurse Exam		X		X			X		
Cardiac/Vascular MRI (A)(B)		X (A1)(B)		X (A2)(B)			X (A3)(B)		
Screening labs (C)	X								
CV Risk Calculator		X							
General Labs (D) (E)		X		X			X		
Biomarker Labs (F)		X		X			X		
Future Research Lab (if pt. consents)		X		X			X		
ALT/AST and CK - Above normal at baseline (G)			X						
Unscheduled ALT/AST/ CK for myalgias/ elevated levels (See Section 5.6)									
Baseline Booklet (H)		X							
6 Month Booklet (H)				X					
12 Month Booklet (H)					X				
18 Month Booklet (H)						X			
24 Month Booklet (H)							X		
Flow Sheet/Addenda		X	X	X	X	X	X		
Phone Contact Form					X	X			
MRI Encounter Form (I)		X		X			X		
Current Med Form		X		X	X	X	X		
Medication Diaries & pill count (J)		Every other month							
Chemo Form	Submit this form after each course (not cycle) of chemotherapy								
RT Form	To be completed when last RT tx. is received or indicating patient will not receive RT.								
Open Label Form	If placed on a statin by their physician. (See Appendix 12 Statin Physician Update)								
Early Withdrawal Treatment/Consent	Submit if patient withdraws from active tx, or withdraws consent prior to end of .study.								

Screening Form	Submit this form every month.	
1 Month Post Contact Form (K)	For patients completing between 24 -27 months of study med – Submit this form 30 days after last dose of study medication.	X

- A1** - Baseline MRI's are required. If a routine standard of care LVEF is obtained by ECHO or MUGA this result should be documented on the flow sheet or the enrollment form.

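### Sections 7.8 and 7.9 give opposite follow-up consequences for the same three reasons, and early drug-stoppers have no scheduled 30-day post-drug contact

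*Combined protocol and SAP*

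**What the plan says.** Section 7.8 lists reasons for stopping study drug other than completing the intervention: "adverse event or serious adverse event, inadequate agent supply, concomitant medications, medical contraindication, or interruption of chemotherapy due to adverse events or death". It then says what follows: "Participants will continue to be followed, if possible, for safety reasons and in order to collect endpoint data according to the schedule of events".

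Section 7.9 lists reasons for leaving the study altogether, among them "adverse event/serious adverse event, lost to follow-up, concomitant medication, medical contraindication, withdraw consent, or death". The wording is permissive.

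Some cases have their own rule. In section 5.6.1, recurrent grade 2 or 3 myalgia, or myalgia with raised enzymes, leads to: "Patient will be considered off study medication but will continue to be followed". For suspected rhabdomyolysis, compartment syndrome or tendon rupture it says: "Patient will remain on study (off study medication) and be followed as usual". The later paragraphs of 7.9 keep a patient who starts an open-label statin in all other parts of the trial. Section 6.9 Step 4 goes the other way: a patient unblinded for toxicity leaves the study and is not followed.

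The form for the 30-day post-drug contact is described in the 7.7 table as "For patients completing between 24 -27 months of study med". The Schema and sections 3.1, 4.4, 7.1, 7.5 and 11.1 restrict it in the same way.

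On when data collection ends, section 4.4 says "After the Final assessment, the patient is no longer followed and data is no longer collected", while section 7.5 says "After the 25 month contact, the patient is no longer followed and data is no longer collected from the patient". Section 3.1 and note K of 7.7 run to 30 days after a last dose that can fall as late as month 27.

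**The concern.** Whether a patient who stops drug for an adverse event, an interacting medicine or a contraindication still has a final MRI can depend on which of two adjacent sections the site reads. These reasons may be related to treatment and to cardiac outcome. Section 12.3 analyses all randomised patients, and 12.7 says that those who drop out early for a possibly statin-related event still inform the primary endpoint. A patient taken off study under 7.9 has no 24-27 month LVEF and cannot contribute one to the ANCOVA.

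On safety, the patients who stopped early are the ones not offered the contact that completers receive 30 days after their last dose, so a persisting or late non-serious event may go unasked about for some months. The three different end dates leave a site unsure how long it must collect data on an extension patient.

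**Working it through.** The point is mainly textual, so the sections are set side by side first.

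**1. The overlapping reasons**

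| Reason | 7.8 | 7.9 | More specific rule elsewhere |
|---|---|---|---|
| Adverse event | Drug stops; follow-up continues where feasible | May leave study | 5.6.1 keeps myalgia and suspected rhabdomyolysis cases in follow-up. 5.6.2.2 (raised ALT, AST or CK) orders laboratory tests 6 weeks after stopping but is silent on study status. 6.9 Step 4 ends follow-up after unblinding. Other events: none |
| Concomitant medication | Same | Same | 7.9 keeps open-label statin users in the trial. Prohibited interacting drugs (5.5): none |
| Medical contraindication | Same | Same | None (5.4 lists contraindications, not what follows) |

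The unresolved cases are other adverse events, enzyme elevations without myalgia that are not re-challenged, interacting drugs other than statins, and contraindications.

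**2. Post-drug contact for an early stopper**

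The scheduled assessments are at 6, 12, 18 and 24-27 months. A patient who stops drug just after one of them and stays on study waits up to 12 − 6 = 6 months for the next (27 − 18 = 9 months if the last one falls at month 27). The exceptions are the 6-week recheck in 5.6.2.2 and the Section 10 window for serious events. That window is 30 days counted from completion of the study, a date not defined for an early stopper.

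**3. End of data collection**

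For a last dose at month 27, the 30-day contact falls at about month 28. The cut-off in 7.5 is month 25, which is 27 − 25 = 2 months before the last dose and 28 − 25 = 3 months before the contact. Under 7.7 the final MRI for this patient falls within 30 days before the last dose, that is, after month 25.

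**4. The plan's own figures, and what they can tell us**

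Inputs from 12.6: SD 7.7, r = 0.5, two-sided alpha 0.05, 80% power, n = 100 per group. Detectable difference = 7.7 × √(2 × (1 − 0.25)) × (1.96 + 0.842) / √100 = 2.64, as tabulated. Enrolment: 200 / (1 − 0.28) = 278, as stated. These figures are not in dispute.

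The documents give no rate of 7.9 removals, so what follows rests on assumed rates.

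- If the removals fall within the budgeted 28%, power is unchanged and bias is the only issue.
- If they come on top of it, n per arm = 278 × (1 − 0.28 − extra) / 2:

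| Assumed extra loss | n per arm | Detectable difference | Power for 2.64 |
|---|---|---|---|
| 5% | 93 | 2.74 | 77% |
| 10% | 86 | 2.85 | 74% |
| 15% | 79 | 2.97 | 70% |

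- Bias: if a fraction f of one arm is removed and its mean LVEF differs by D from those who remain, the unadjusted arm mean shifts by f × D. For f from 0.05 to 0.15 and D from 2.64 to 7.7 points (both ranges assumed), the shift runs from 0.05 × 2.64 = 0.13 to 0.15 × 7.7 = 1.16 points. Equal removals with equal D in both arms would cancel.

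**The case against.** A reader might infer that patients who stop because of harm lose their safety and endpoint follow-up. The documents do not say that. Section 7.9 permits removal and does not require it. Section 7.8 directs continued follow-up, 5.6.1 keeps the main muscle toxicities in, and the open-label paragraph covers patients whose physician starts a statin, an evident route to a concomitant-medication stop. A patient who stops drug but stays on study keeps every later assessment. The only mandatory loss is in 6.9 Step 4.

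Nor are early stoppers without any check. Section 5.6.2.2 provides the 6-week recheck, note J of 7.7 a pill count at discontinuation, and 11.1 an Early Withdrawal Form within 14 days. Section 10 requires grade 4 and 5 serious events to be reported regardless of attribution. Section 12.4 anticipates informative missingness. The 25-month sentence looks like a leftover from before the extension, since 7.4 and the 7.7 table carry the 24-27 month assessments.

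Most of this stands and narrows the point. It does not remove it. For the cases with no specific rule, permissive wording leaves to the site whether outcome data exist. Serious-event reporting centred on grades 4 and 5 does not replace a scheduled question about a persisting moderate event. The one approach 12.4 describes conditions on baseline characteristics and treatment assignment, so it cannot use the post-baseline event that led to removal.

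**Conclusion.** The concern holds in limited form, as a should-fix. Sections 7.8 and 7.9 conflict on three reasons, and the conflict is live only where no more specific rule decides. There, a site following the protocol as written can lose safety data and the final LVEF for reasons linked to treatment, contrary to the intent of 12.3 and 12.7. Early stoppers lack the scheduled 30-day contact that completers receive, and the end of data collection needs one definition.

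The size cannot be stated. A reader might take the 78 expected drop-outs (278 − 200) as the number affected, but that figure counts patients expected to be missing at the end, not early drug-stoppers. Some of the 78 could not be telephoned, and early stoppers who stay in follow-up are not among them. A reader might also conclude that harm is hidden or the LVEF comparison biased. The documents support only a risk: they give no removal rate, no difference between arms and no direction. The power and bias figures in the working depend wholly on assumed rates.

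**What to change.** - In 7.9, remove adverse event, concomitant medication and medical contraindication from the off-study reasons. These patients then stay in follow-up under 7.8 unless they withdraw consent, are lost or die.
- Reconcile 6.9 Step 4 with the edited 7.9, which it would otherwise contradict: either patients unblinded for toxicity remain in data collection, or they are named as an explicit exception.
- In the Schema and sections 3.1, 4.4, 7.1, 7.5, 7.7 (table row and note K) and 11.1, apply the existing 1 Month Contact Form 30 days after the last dose to every patient still in contact, whenever drug stops.
- In 4.4 and 7.5, replace the two closing sentences with one end of data collection: the later of the final assessment and 30 days after the last dose. In Section 10, define the start of the serious-event window for early stoppers.

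The cost is amendment wording and one telephone contact per early stopper, on a form that already exists; the documents do not give the number of early stoppers. The change concerns data collection only and alters no dosing or drug-stopping rule.

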8. PROTOCOL SPECIFIC TRAINING REQUIREMENTS

8.1 MRI Training

- Refer to the “Helpful Guides” located on the Research Base website in the Appendices section.
- The study PI presented the MRI protocol for review and discussion with the MRI technologists and associated study coordinators during the Investigator meeting held at the 2013 Annual Research Base NCORP Meeting.

Prior to the start of participant enrollment into the study, Wake Forest University Medical Center cardiology imaging specialists observe and continue MRI training at each of the study locations.

Each site will be required to submit 2 satisfactorily performed studies to the image coordinating center at Wake Forest before initiating the study.

8.2 NEUROCOGNITIVE TRAINING

8.2.1 Certification Requirement

Certification for the administration of the neurocognitive battery and questionnaires will include self-study, internet-based training, didactic presentations, role-played administrations, and Q&A and feedback. All training will be supervised by experienced test administrators ([name] at WFUSM, [name] RN OCN, Site Coordinator or other trained/certified administrator who will be responsible for certifying test administrators.) They will also be responsible for helping staff maintain certification by having regular meetings to discuss the procedures and providing supplemental training as needed.

Bilingual staff must be certified to administer neurocognitive battery to non-English speaking patients. Certification procedure must be completed by staff prior to patient enrollment.

8.2.2 Certification Procedures

All neurocognitive assessments will be conducted by trained and certified research personnel. Training and certification procedures must be completed by research staff prior to patient enrollment. Certification for administration of the neurocognitive battery will include viewing of a training video on the Wake Forest University Health Sciences website, reviewing the content of the protocol-specific test booklets including all aspects of administration and scoring, a didactic presentation of each test and questionnaire to be administered, and role-playing of administrations with Q&A and feedback. All training will be supervised by experienced test administrators ([name], psychologist and co-PI of this study, and other trained/certified administrators designated by the WF NCORP Research Base.)

There are 3 ways to become certified: 1) Training and certification on-site by WF NCORP certified personnel, contact [contact]; 2) Training and certification at the annual meeting of the WF NCORP Research Base, held each fall (contact the Research Base Administrative Secretary at [contact] for date of next meeting; 3) By sending in a recorded presentation and administration booklet to [contact] for

certification review. Alliance sites that have current credentialing for Alliance neurocognitive studies may choose #3 for WF certification.

Periodic re-certifications will be required if it has been more than 6 months since the staff member administered the tests. This procedure has been successfully used in our studies of cognitive effects of cancer and its treatments as well as by [name] and his team in large scale, multi-site clinical trials and observational studies (e.g., WHIMS, CoSTAR, SPRINT, Look AHEAD, LIFE, MESA).

9. SPECIMEN MANAGEMENT

9.1 Storage of Blood for Future Research Testing (if applicable)

At baseline, 6 months and 2 years an additional 2 tubes of blood will be collected on patients who have given consent to store blood for future research testing.

These future tests may include searches for combinations of genetic nucleotide polymorphisms that are associated with susceptibility to a fall in LVEF in patients receiving chemotherapy. At present, planned testing is not specified and thus not included in our specific aims. All blood samples will be de-identified and stored in LabCorp's Bio-repository located in Greenfield, IN. Only researchers approved by [name], the principal investigator at Wake Forest School of Medicine will receive the sample. Lab supplies and instructions for blood stored for future research testing will be provided by LabCorp. (See Appendix 10 for further lab instructions).

Labs for future research testing should not be drawn and sent to LabCorp until specific consent for future research testing has been verified and eligibility established.

9.2 Lab Corp: Routine Labs required Per Protocol

Lab Corp will be utilized for all labs. LabCorp couriers will deploy to each site from local LabCorp facilities for specimen pick-up as samples are drawn. All specimens should be collected in containers provided by LabCorp. Note storage times and temperature instructions for each test.

Eligibility and baseline labs (Cholesterol, LDL, HDL, Triglycerides, Glucose, Creatine Kinase, TSH, ALT, AST, Total Bilirubin, Hematocrit [only if gadolinium contrast is to be administered for the MRI procedure] and BHCG if applicable) will be drawn and analyzed by LabCorp. Once eligibility has been determined the remaining protocol labs (Hematocrit preferred within 8 hours but acceptable to within 40 hours of MRI for patient's receiving gadolinium contrast) CRP, Troponin 1, Aldosterone, IL-6, TNF-a, and Renin will be drawn and sent to LabCorp.

9.3 Collection and Handling Procedures

Refer to Appendix 10 for instructions.

10. REPORTING ADVERSE EVENTS

- A list of serious adverse events that have occurred or might occur that are related to this study intervention can be found in Section 6.2.
- Serious Adverse Event reporting begins after the informed consent is signed.
- Serious Adverse Events occurring within 30 days of study completion must be reported via FDA Form 3500 (MedWatch).

